Access to Intensive Treatment. Half of the participants who meet initial eligibility for intensive treatment will be randomized to have access to intensive treatment, with patient choice among intensive treatments (if eligible for both standard dosing of a 12-week regimen of varenicline and combination nicotine patch and mini-lozenge). At the time a patient requests treatment, the Tobacco Care Manager will send a medication order for the patient’s primary care provider to review and order, if the primary care provider considers this a safe and appropriate medication for the patient. Intensive treatment will involve three 15-minute phone counseling sessions delivered 1 week prequit, on the day after the target quit day, and 1 week postquit, following a standard protocol (see uploaded Cessation Counseling Protocol). These sessions will be offered by bachelor’s level UW-CTRI Health Counselors. The remaining half of the experimental sample will be randomly assigned to standard care (referral to the Primary Care Provider and referral to a tobacco quit line, which for Wisconsin residents comprises a single 20-minute proactive cessation counseling call from a trained quit coach and, if medically eligible, a 2-week supply of a nicotine monotherapy dispensed by the quit line, at no cost to the smoker). Data from the WTQL will note the patient’s quit date, counseling use, and medications dispensed for those referred to the WTQL. Quit line use will also be assessed via self-report at semi-annual follow-ups.

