3. Post-quit attempt assessment (See uploaded Post Treatment Follow-Up assessment). Those who request smoking cessation treatment through a Care Manager will be asked to complete 10-20 minute telephone interviews 3, 12, and 26 weeks post-target-quit day and paid \$10 for these calls (this payment is low to avoid interfering with the incentive manipulation). At these follow-ups, patient self-report of smoking, treatment use, and quitting attitudes, beliefs, and experiences (including withdrawal and social support related to quitting) will be assessed, along with any adverse events that occurred since the beginning of cessation treatment. In addition, participant utilization of treatment will be assessed by tracking how many calls or visits the participant completed and how much medication they report using.

To enhance intervention fidelity, intervention delivery will be assessed via supervisory review of recorded motivational interventions by the Care Manager and smoking cessation counseling calls delivered by UW-CTRI Health Counselors, with feedback regarding performance to enhance fidelity, as needed.

To enhance follow-up interview and visit completion rates, participants will be texted, mailed, sent MyChart reminders or automated phone calls (depending on their communication preferences as noted in the EHR and during enrollment).

Data management, transmission and storage

Data will be transferred from the EHR to research databases for use in tailoring and personalizing outreach (as randomly assigned) and tracking recruitment, participant healthcare utilization, smoking cessation treatment, and changes in smoking status, insurance type, or health status over the course of the 2-year study. Both healthcare systems maintain secure, HIPAA-compliant electronic health records for their operations and have mechanisms and processes in place to extract and encrypt data from the EHR for research purposes. Staff at UW-CTRI will receive data on enrollees who have provided consent for such data sharing as

part of the oral consent process. The data to be extracted from the EHR for the purposes of reach-focused interventions and assessment are shown in the uploaded List of EHR Data to Be Extracted. The research office will also receive data from the Wisconsin Tobacco Quit Line regarding services those in Standard Care received (i.e., did they complete the counseling call, were they sent any smoking cessation medications).

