Although this program will evaluate interventions delivered by healthcare system personnel (Tobacco Care Managers), delivery of intensive treatment and follow-up data collection procedures and collation of data from multiple sources/sites necessary for thorough program evaluation are the responsibility of the UW-CTRI study investigators. To achieve the study aims, UW-CTRI investigators require access to identifiable patient data. At UW-CTRI, all study data will be stored in a HIPAA-compliant and secure manner on Department of Medicine servers with UW-CTRI-controlled password access. Staff trained in human subjects research and HIPAA compliance will link these datasets using a random subject identifier and will then de-identify the data for analyses.

Treatment procedures description

The reach-focused interventions to be evaluated in this study will be delivered by healthcare system Tobacco Care Managers and/or UW-CTRI personnel. In addition to recruiting, screening, consenting, randomizing, and informing enrollees about available treatments at enrollment, healthcare system Care Managers will be responsible for live outreach via telephone to provide motivational interventions to promote cessation and treatment use (as randomly assigned), and to coordinate care for participants who request smoking cessation treatment during the study (including seeking approval of medications by primary care providers and updating patient records to reflect treatment use and changes in smoking status). UW-CTRI personnel and health system Care Managers will work together to prepare and disseminate automated semi-annual mailed/electronic outreach materials (e.g., UW-CTRI personnel will mail letters, but Care Managers who have access to the EHR patient message portal will need to send MyChart messages). UW-CTRI personnel will be responsible for conducting follow-up interviews, including semi-annual interviews and post-target-quit-date follow-up interviews, and will alert Care Managers to any requests for treatment that occur during these telephone interviews. UW-CTRI Health Counselors will track completion of intensive treatment counseling calls and use of quit line services to determine whether or not a patient in the incentive condition is owed a \$40 incentive. UW-CTRI staff will process incentive payments and letters (see uploaded Incentive Letter).

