Aim 1. To develop an optimized package of health system interventions to promote smoking cessation treatment reach among patients not initially willing to quit, logistic regression analyses will be conducted with binary treatment initiation over 1 year of study enrollment as the primary outcome, in the primary sample randomized on all 4 experimental factors. Effect size estimates will be generated and all main and all 2-way, 3-way, and 4-way interactive effects will be tested as predictors in the logistic regression model. In addition, the magnitude of the difference in treatment initiation rates between the most promising intervention conditions and the cell in which all the intervention components are off will be used to generate an upper limit estimate of optimized reach intervention package effects. Exploratory analyses will be conducted adjusted for covariates known to be predictive of treatment use. Exploratory sensitivity analyses will be conducted to estimate intervention component effects across a range of assumptions regarding missing outcome data. We anticipate that 25% of follow-up data will be missing and will examine the robustness of results across intent-to-treat and less stringent assumptions regarding missingness (i.e., that 90%, 80%, or 70% of missing cases are smoking) in sensitivity analyses. We may also use multiple imputation and examine the consistency of results across multiply imputed datasets and those imputed using the simple methods already described. This analysis will use data collected via UW-CTRI staff during follow-up telephone interviews supplemented by data regarding smoking cessation attempts and treatment utilization extracted from the EHR and the WTQL.

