Aim 2. To assess the cumulative main and interactive effects of each intervention component on binary treatment initiation over 2 years of study enrollment, logistic regressions predicting any treatment initiation (defined as completing a first counseling session, the primary outcome at a more distal endpoint) will address this aim, first in the ~240-300 patients (max 300) eligible for intensive treatment to examine all 4 intervention components, and then, separately, in the ~30-60 (max 60) participants who do not meet criteria for access to intensive treatment. As in the analyses for Aim 1, effect coding will be used to ensure the independence of the main and interactive effects in this balanced design, exploratory analyses will be conducted with adjustment for covariates, and exploratory sensitivity analyses will examine the robustness of results across a range of missing data assumptions.

In addition to the binary logistic regression described above, exploratory logistic regression models will estimate intervention component main and interactive effects on treatment completion (all 3 counseling sessions and medication initiation) among those randomly assigned to have access to intensive treatment with C-NRT or varenicline and counseling. This exploratory analysis will quantify the effects of the informational/motivational intervention components on the dose of evidence-based treatment received by participants over 2 years. Effect coding, covariate adjustment, and sensitivity analyses will be used, as described above. Exploratory descriptive analyses of the frequency and temporal patterns of treatment use will also be conducted (e.g., to explore whether C-NRT use tends to follow varenicline more often than the reverse, to see whether C-NRT is more likely to be repeated than varenicline use). As for Aim 1, this analysis will use data collected via UW-CTRI staff during follow-up telephone interviews supplemented by data regarding smoking cessation attempts and treatment utilization extracted from the EHR.

Secondary Aim 1. Although the primary outcome in this study is treatment reach, the ultimate objective of this project is to help more smokers stop smoking. A key secondary binary logistic regression analysis in this project will estimate reach-focused intervention component effects on end-of-study 7-day point-prevalence abstinence confirmed by CO testing, and, if CO is elevated,

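### The missing-data scenarios for treatment initiation are stated as shares smoking, and none lets missing initiation differ by factor level

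*Combined protocol and SAP*

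**What the plan says.** **Outcome.** The Analysis Plan of the combined protocol and SAP takes "binary treatment initiation over 1 year of study enrollment as the primary outcome" for Aim 1. Aim 2 uses the same outcome over 2 years: "any treatment initiation (defined as completing a first counseling session, the primary outcome at a more distal endpoint".

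**Missing data.** Under Aim 1 the plan expects 25% of follow-up data to be missing. It will compare results under "intent-to-treat and less stringent assumptions regarding missingness (i.e., that 90%, 80%, or 70% of missing cases are smoking". It adds: "We may also use multiple imputation and examine the consistency of results across multiply imputed datasets". No imputation model is given. Aim 2 says only that "exploratory sensitivity analyses will examine the robustness of results across a range of missing data assumptions". All of this is labelled exploratory. The monitoring paragraph at the start of the Analysis Plan foresees adjusting for retention differences by patient, clinic and Care Manager; it does not name the experimental factors.

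**How initiation is recorded.** The Aim 1 text draws on interviews, the EHR and the Wisconsin quit line (WTQL).
- Treatment procedures description: "UW-CTRI Health Counselors will track completion of intensive treatment counseling calls and use of quit line services". The same sentence gives the purpose, which is to decide whether a participant in the incentive condition has earned the $40.
- Access to Intensive Treatment (section F): quit line data cover "counseling use, and medications dispensed for those referred to the WTQL", and interviews add self-reported quit line use.
- Data management, transmission and storage: for standard care, the quit line reports "did they complete the counseling call, were they sent any smoking cessation medications".
- Data Safety and Monitoring Plan: counseling completion is checked monthly against incentive payments.

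**Mail-back form.** Under the semi-annual assessment, people not reached by phone at 12 or 24 months get a form covering smoking status and treatment over the previous 6 months only.

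**The concern.** Smoking status does not determine initiation. Someone who completes a counseling call and keeps smoking is both a smoker and an initiator, so a statement that 80% of missing cases smoke does not tell the analyst what to enter for the primary outcome. The percentages look built for abstinence. Their complement, 10-30% not smoking, lies within the 5-30% abstinence range in Power and Sample Size, whereas treatment use there ranges over 5-65%.

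The second gap is that each scenario applies one value to every missing case, although initiation may not be recorded equally well at each level:
- *Intensive access.* Intensive sessions are delivered and logged by study staff. Standard-care calls are captured through quit line data for people who were referred. Self-referred calls, calls to another state's quit line and other outside counseling may rest on self-report.
- *Incentives.* Tracking and monthly reconciliation exist to support payment, and a participant owed $40 has a reason to make a completed call known.
- *Care-manager calls (possibly).* Participants on this level have up to five extra live conversations about treatment with staff who also update treatment use in the record.

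The July 2022 update makes effect-size estimates, and the choice of promising components from them, the trial's product. A sensitivity analysis that cannot show how an estimate depends on who is observed would give unearned reassurance.

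**Working it through.** **Inputs from the documents.** 25% missing follow-up data, not split by level (Aim 1); an 8-point increment and base rates of treatment use of 5-65% (Power and Sample Size); N = 300 at most, so 150 per level of a factor (July 2022 update).

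**Assumptions, not in the documents.** Initiation of 20% with a component off and 28% with it on; 0-30% as the range for the fraction initiating among unresolved people; an unresolved share that depends on level only as shown.

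**The plan's own figure.** It gives none for the effect of missing data. The nearest is main-effect power above .9 at N = 1664. With 832 per level, two-sided alpha .05 (sidedness assumed) and +8 points, power is 0.9999 at a 5% base, 0.9423 at 65% and at lowest 0.9045 (46% base). That reproduces; nothing below depends on it.

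**Case A: records stand, but some people without a recorded initiation lack full follow-up coverage.**
Rate at a level = r + u × q, where r is recorded initiation, u = c × (1 - r) is the unresolved share, c is the share without full coverage and q is the fraction of unresolved people who initiated.
- c = 0.25: u1 = 0.25 × 0.72 = 0.18 and u0 = 0.25 × 0.80 = 0.20 (27 and 30 of 150).
- Common q: the difference is (r1 - r0)(1 - c × q), which is always positive here.

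| Common q | On | Off | Difference | Odds ratio |
|---|---|---|---|---|
| 0 | 0.280 | 0.200 | +8.0 | 1.56 |
| 0.1 | 0.298 | 0.220 | +7.8 | 1.51 |
| 0.2 | 0.316 | 0.240 | +7.6 | 1.46 |
| 0.3 | 0.334 | 0.260 | +7.4 | 1.43 |

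- Level-specific q: on 0, off 0.3 gives 0.280 - 0.260 = +2.0; on 0.3, off 0 gives 0.334 - 0.200 = +13.4.
- Tipping point with q = 0 on: q off = 0.08 / 0.20 = 40%.

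**Case B: the outcome is wholly missing for a share m at each level.**
Rate = (1 - m) × p + m × q, where p is initiation among those observed.
- m = 0.25, common q: 0.75 × 8 = +6.0 points, whatever q is.
- m = 0.25, on 0, off 0.3: 0.210 - 0.225 = -1.5; on 0.3, off 0: 0.285 - 0.150 = +13.5.
- The difference vanishes when q is 0.75 × 0.08 / 0.25 = 24 points higher with the component off.
- m = 0.10: 0.252 - 0.210 = +4.2 and 0.282 - 0.180 = +10.2. Reversal within 0-30% needs m > 0.08 / 0.38 = 21%, which the plan's 25% exceeds.

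**Scale.** The 95% sampling margin at N = 300 is 1.96 × √(0.28 × 0.72/150 + 0.20 × 0.80/150) = ±9.6 points.

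**Mail-back form.** If 25% are missed at each interview, between 0.25² = 6% (independent misses; about 19 of 300) and 25% (the same people; 75 of 300) miss two in a row. Only those who return the form and had earlier counseling found in no record are affected; that number is not known.

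**The case against.** The plan is not empty on this point. It commits to a range of assumptions and allows multiple imputation. By its place in the list, intent-to-treat can be read as the strict end, with all missing cases smoking; the analogue for initiation is that nobody missing initiated. A competent analyst could reach that rule unaided, and level-specific tipping points are one reasonable choice among several. Records also reduce the unresolved share. All of this stands, and it limits the severity. It does not supply a value for a missing initiation outcome or a scenario that varies by level.

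Three stronger readings should be resisted.
- A reader might infer that only the intensive-access factor is exposed. The payment purpose of tracking and the monthly reconciliation point to incentives as well, and the care-manager contacts may matter too.
- A reader might take 25% as the share with no initiation outcome and so expect a sign reversal. The 25% refers to follow-up data in general; EHR, quit line and counselor records supplement the interviews, and no rate is given for initiation itself.
- A reader might compound two missed year-1 interviews to 1 - 0.75² = 44% without full coverage. That requires a six-month recall window in the telephone interview; the documents state such a window only for the mail-back form.

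**Conclusion.** The point holds on the text with high confidence: the numeric scenarios concern smoking, the outcome is initiation, and no scenario differs by level of any factor. The consequence is less certain. Under the assumed 28% vs 20%, level-specific variation at 25% moves the estimate by up to 6 points from +8.0 in Case A, and over -1.5 to +13.5 in Case B, whereas common values barely move it. Which case is nearer the truth depends on an unresolved share that the documents do not give. The Case A shift lies within the ±9.6-point sampling margin, the plan already disclaims adequate power, and the documents do not establish the direction of any bias. This is a minor, cheap correction, not a threat to the design.

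**What to change.** For Aims 1 and 2:
1. Replace the smoking scenarios with the fraction initiating among participants who have no recorded initiation (study, quit line or EHR) and incomplete follow-up coverage of the outcome window.
2. State that 0%, counting these people as non-initiators, is the intent-to-treat rule.
3. Report the size of this group by level of each of the four factors.
4. Vary the fraction, for example over 0-30%, first in common and then independently by level of each factor, and report the tipping point.
5. If multiple imputation is used, include the four factors in its model.
6. Keep the 90/80/70% smoking scenarios for abstinence.

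Secondary: have the 12- and 24-month mail-back form ask about treatment since enrollment or the last completed interview, and record which form version was used.

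Cost: a few sentences in the analysis plan, a few extra runs and one changed question. The downsides are slightly longer recall on the form, and mixed recall windows if it changes mid-study.

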Design Overview. In this factorial experiment (see Table 1), participants (not willing to enter cessation treatment at the time of enrollment) recruited by phone after initial outreach or primary care visits in or telemedicine appointments with participating clinics in UW Health and AdvocateAurora Health will be screened, consented, and randomized over the phone to one of 16 conditions resulting from the crossing of the 4 experimental factors in this 2 (incentives on vs. off) x 2 (tailored vs. generic outreach letters) x 2 (care manager calls on vs. off) x 2 (access to intensive treatment on vs. off) design. Participants who request treatment for smoking cessation over the next 2 years will do so through a Tobacco Care Manager who will coordinate referrals to a tobacco quitline (the Wisconsin Tobacco Quit Line (WTQL) for Wisconsin residents) and/or the patient's primary care provider, as preferred by the patient in the standard care conditions. Tobacco Care Managers will also coordinate scheduling with a UW-CTRI Health Counselor for intensive smoking cessation treatment. Participants will have access to either standard or intensive smoking cessation treatment for 24 months, and will receive outreach promoting smoking cessation twice per year from enrollment to 22 months post-enrollment. Participants will be asked to complete brief (10-20-minute) follow-up telephone interviews 6, 12, 18, and 24 months after enrollment. Those claiming abstinence at the 12- and 24-month post-enrollment phone interviews will be asked to return to their primary care clinic to complete breath, urine, and/or saliva testing to verify abstinence from combustible tobacco. This will entail providing breath samples for carbon monoxide testing and/or a urine or saliva sample for immediate cotinine/anabasine testing (no samples will be stored). Participants may also be asked to collect a saliva sample at home and return it in the mail. If a participant sets a target stop-smoking date as part of a smoking cessation treatment episode (either standard or intensive treatment), the participant will be asked to complete telephone follow-up interviews 3, 12, and 26 weeks post-target-quit-day, as well. Participation in the study will last 24 months (27 months maximum, if the person is not reached immediately for the final 24-month post-enrollment telephone follow-up or visit). In addition, data on health status and healthcare utilization for participants who do vs. do not use stop-smoking treatment and quit smoking will be extracted from the EHR for up to 1 year pre-enrollment, and 4 years post-enrollment to inform economic analyses for Aim 3 and moderation analyses for Aim 4.

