Some participants will receive additional or modified outreach, as randomly assigned. Some will receive incentives to use smoking cessation counseling, some will receive automated tailored letters and MyChart messages (if MyChart active) promoting smoking cessation treatment use, and some will receive a motivational intervention and care management delivered by phone. These experimental interventions are described in detail below.

Incentives. In 2 of our recent studies^{45,46}, incentive-driven increases in counseling use mediated incentive effects on abstinence in Medicaid-insured smokers. Given the significant savings associated with smoking cessation⁴⁷, modest incentives *to use treatment* may well be cost-effective if they drive increased quitting. Modest incentives (\$25 or \$50) also improve attendance at primary care visits⁴⁸. Thus, evidence supports modest, utilization-contingent incentives for use of both smoking cessation and primary care treatment. The proposed project will be the first to examine incentives to use smoking treatment (rather than achieve abstinence) in primary care.

Half of participants will be assigned to receive incentives while the other half will not. Incentives will be tied to readily observable *initiation* of treatment (i.e., completion of a quitline or health counselor counseling call). A single \$40 incentive *per round* will be offered to spur treatment initiation. The \$40 incentive was selected based on the promising results of earlier work that

used \$30 incentives to improve counseling completion, and through this pathway, abstinence rates among low-income smokers. A slightly larger incentive will be used here due to the greater diversity in socioeconomic status of the proposed sample, and because only 1 incentive is available per treatment round. Participants will be limited to 2 rounds of treatment per year (as per Affordable Care Act guidelines⁴⁹), for a maximum of \$160 over the 2-year study. Participants will be paid by mailed check or gift card. Incentives are not contingent on medication use, as medication use is subject to medical eligibility and too difficult to verify. Those in the incentive condition will be told of these incentives at enrollment and reminded of them at months 6, 12, 18, and 22 post-enrollment.

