Healthcare system Tobacco Care Managers will deliver the reach-focused interventions in this study. For those who tell the Care Manager that they are ready to quit within 30 days at any point during the 24-month follow-up period, the Care Manager will coordinate access to either standard care (quit line and/or primary care provider referral) or intensive smoking cessation treatment depending on experimental condition. Coordinating standard care means providing referral to a state quit line (typically the Wisconsin Tobacco Quit Line), for patients who agree to this, and/or sending a message to the patient's primary care provider in the EHR to let the provider know the patient wants help in quitting smoking. Coordinating intensive treatment means screening for current eligibility for varenicline or combination NRT and obtaining oral consent for intensive treatment. For those who consent, the Care Manager will schedule a first session with an UW-CTRI health counselor and send a request for Primary Care Provider review for varenicline or combination NRT.

UW-CTRI personnel will be responsible for: conducting telephone follow-up interviews 6, 12, 18, and 24 months post-enrollment; conducting in-clinic visits with patients to verify claimed abstinence 12- and 24-months post-enrollment via biochemical testing (breath CO, urine, and/or saliva testing without biobanking); delivering three sessions of telephone counseling to those in the intensive cessation treatment conditions who initiate treatment; and conducting telephone follow-up interviews 3, 12, and 26 weeks after a patient's target quit day (for those who set a quit day during the study).

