salivary cotinine/anabasine testing, among those claiming abstinence. This analysis will estimate the main and interactive effects of the intervention components on end-of-study (2-year) 7-day point-prevalence abstinence rates (as ascertained by self-report and biochemically confirmed). The primary analysis will be an unadjusted, intent-to-treat analysis, but this will be followed by exploratory adjusted models and sensitivity analyses. This analysis will use data collected by personnel during the final semi-annual follow-up telephone interview plus the biochemical confirmation visit (for those claiming abstinence), supplemented by data on smoking status extracted from the EHR.

Additional, exploratory analyses will examine the 7-day point-prevalence abstinence rates at 3 time points following each round of treatment initiated with the Tobacco Care Managers (3, 12, and 26 weeks post-target-quit-day), for up to 4 rounds of treatment. Exploratory descriptive analyses will summarize abstinence rates at each time point, and the effects of intervention components on these abstinence rates will be explored, both within and across rounds of treatment. This analysis will use data collected by UW-CTRI personnel during the post-quit follow-up telephone interviews.

Secondary Aim 2. The degree to which intervention component effects on abstinence are mediated by treatment use will be examined via formal mediation analysis. These tertiary outcome models will examine the extent to which intervention component effects on 7-day point-prevalence abstinence after 2 years of enrollment are mediated by initiation of treatment in the preceding 2 years. Enrollees eligible for intensive treatment will be the primary sample for these analyses, with exploratory replication in those not eligible for intensive treatment. To examine mechanisms of specific intervention effects on the primary outcomes of interest, additional, exploratory models will examine the extent to which intervention components affect quitting motivation, self-efficacy, and perceived intra-treatment social support, and the degree to which these candidate mediators are associated with treatment initiation and point-prevalence abstinence at the end of the study. Within each treatment episode, the degree to which short-term abstinence (3-, 12-, or 26-weeks postquit) is mediated by reductions in withdrawal will also be explored.

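### Exploratory component effects on abstinence 3, 12 and 26 weeks after a quit day compare only people who sought treatment, and overlapping treatment rounds have no analysis rule (minor)

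*Combined protocol and SAP*

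**What the plan says.** The additional analyses under Secondary Aim 1 (Analysis Plan) examine "7-day point-prevalence abstinence rates at 3 time points following each round of treatment initiated with the Tobacco Care Managers", for up to four rounds. Descriptive summaries come first. Then "the effects of intervention components on these abstinence rates will be explored, both within and across rounds of treatment". The source is stated: "This analysis will use data collected by UW-CTRI personnel during the post-quit follow-up telephone interviews". No denominator, model or estimand is given for the component effects.

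Who gets these calls is described in three places:

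- Assessment Plan, item 3: "Those who request smoking cessation treatment through a Care Manager will be asked to complete 10-20 minute telephone interviews 3, 12, and 26 weeks" after the target quit day.
- Methods, Design Overview, as the condition for the calls, under standard or intensive treatment: "If a participant sets a target stop-smoking date as part of a smoking cessation treatment episode".
- Section G, on the tasks of the research staff: the calls are "for those who set a quit day during the study".

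Aim 2 defines treatment initiation as a completed first counseling session. Initiation is the primary outcome, at 1 year (Aim 1) and 2 years (Aim 2).

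On repeat treatment, Section F (Incentives) says: "Participants will be limited to 2 rounds of treatment per year". The treatment procedures description repeats this limit, adds a total of four, and has Care Managers arrange treatment during the first 98 weeks. Neither place gives a minimum interval between rounds.

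**The concern.** A participant who never seeks treatment has no target quit day and so no 3-, 12- or 26-week outcome. Entry to the analysis is therefore decided after randomization, by the behavior that the components are built to shift. Initiators with a component on and initiators with it off need not be comparable, even though the groups they came from were randomized. Analyses across rounds add a second selection, since entry to round 2 depends on what happened after round 1.

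The second gap is overlap. Each round carries a 26-week follow-up, and two rounds can start within one year. A call scheduled for round 1 may therefore describe the result of round 2, and the same person can contribute several correlated outcomes.

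At stake is the interpretation of an exploratory table. After the July 2022 reduction in sample size, the trial's stated purpose is to produce effect size estimates and identify promising components. A per-initiator contrast with the wrong sign could be read as evidence against a component that helps.

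**Working it through.** **The plan's own figures.** The plan gives no number for the per-round contrasts. The illustration borrows the 8-point increment in reach from Power and Sample Size. The power claim there reproduces: with 1664/2 = 832 per level, +8 points and two-sided alpha .05 (sidedness assumed), power runs from .904 at a 46% base rate to 1.00 at 5%, so it exceeds .9 throughout. The revised sample also reproduces: 240/16 = 15 per cell. The present point does not depend on either figure.

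**Selection: inputs.** All rates are assumptions except the 8-point increment.

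- Reach with the component off, r0 = 10%; on, r1 = 18%.
- Abstinence in people who would initiate anyway, qa = 30%.
- Abstinence in the added initiators when treated, qc = 15%.
- Abstinence without treatment, qn = 5%.
- The component acts only by changing who initiates. It leaves qa unchanged.

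**Among initiators**

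- Off: qa = 30.0%.
- On: (0.10 × 0.30 + 0.08 × 0.15)/0.18 = 0.042/0.18 = 23.3%.
- Difference: −6.7 points. In general it is (r1 − r0)/r1 × (qc − qa).

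**Among all randomized**

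- Off: 0.10 × 0.30 + 0.90 × 0.05 = 7.5%.
- On: 0.10 × 0.30 + 0.08 × 0.15 + 0.82 × 0.05 = 8.3%.
- Difference: +0.8 points. In general it is (r1 − r0) × (qc − qn).

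A simulation of 2 million people gave 29.9% vs 23.5% among initiators and 7.5% vs 8.3% overall.

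**Range,** for +8 points of reach from a base of 5% to 30%, with qa = 30% and qn = 5%:

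| Added initiators quit at | Difference among initiators | Difference among all randomized |
|---|---|---|
| 10–20% | −12.3 to −2.1 points | +0.4 to +1.2 points |
| 30% | 0 | +2.0 points |
| 40% | +2.1 to +6.2 points | +2.8 points |

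The sign reverses only when qc lies between qn and qa. At N = 300 (150 per level), 10% vs 18% reach would leave about 15 vs 27 initiators to compare.

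**Overlap.** If the two quit days are g weeks apart, the round-1 call at week w falls w − g weeks after the round-2 quit day.

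- Any g under 26 puts the round-1 week-26 call after the round-2 quit day.
- g = 9: round-1 week 12 is round-2 week 3.
- g = 14: round-1 week 26 is round-2 week 12.
- g = 23: round-1 week 26 is round-2 week 3.

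If two quit days fell at random within a year (assumption), the share under 26 weeks apart would be 1 − (26/52)² = 75%. With an assumed 12-week minimum gap it would be 58%. Overlap is not forced: four rounds spread over 98 weeks can be 98/3 = 32.7 weeks apart.

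**The case against.** The strongest reply is that these analyses are labelled exploratory and nothing important rests on them. Much of that stands. The key abstinence analysis is intent-to-treat at 2 years. Aim 1 builds the package from 1-year initiation and low cost, and the cost per quit in Secondary Aim 3 uses the secondary abstinence outcome. A reader might infer that the per-round rates could distort the choice of package, but no section feeds them into it.

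A reader might also infer that the denominator differs between standard and intensive care because quit days are recorded differently. The documents do not show this. Quit line data do include a quit date, but the Design Overview schedules the calls under either kind of treatment, item 3 covers everyone who requests treatment through a Care Manager, and the Consent section applies one initiation script to all requesters. In the provider-referral route, the Care Manager tells the provider that a quit date has been set, so it is already known.

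On overlap, 7-day point prevalence is a status on a date. A re-treated person who is abstinent at round 1's week 26 is truly abstinent then, so the result is not false. What is missing is a rule for attributing it and for handling several rounds in one person. The optional GEE under Supplemental Models covers the semi-annual waves, not rounds. The uploaded treatment-initiation form, not available here, might contain a minimum gap.

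None of this answers the selection problem: the plan still intends to explore component effects in a group formed after randomization.

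**Conclusion.** The point holds, at minor severity and for this exploratory analysis only. As written, the per-round component contrasts are not randomized comparisons, and no rule covers overlapping or repeated rounds.

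The direction of bias is not known. It would be wrong to conclude that components raising reach must look harmful. That happens if added initiators quit less often than those who would have initiated anyway, which is plausible in people enrolled because they were unwilling to quit soon, but the documents give no data on it. With equal quit rates the bias is zero in the illustration; with higher rates it runs the other way. The sizes rest on assumed rates and on a component that works only through reach. Access to intensive treatment also changes the treatment itself, so the illustration does not carry over directly to that factor. How often rounds will overlap cannot be determined from the documents.

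**What to change.** Amend the exploratory paragraph of Secondary Aim 1:

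1. Report per-round abstinence among initiators descriptively, without component effects. State once whether that group means requested treatment, set a quit day, or completed a first session.
2. Base any component effect on abstinence on all randomized participants, using the semi-annual follow-up data already collected. The GEE under Supplemental Models is a suitable vehicle.
3. If an outcome per randomized patient is also built from post-quit calls, with non-initiators scored as not abstinent, label it treatment-assisted abstinence and note that it ignores unaided quitting. On the assumptions above it gives 0.10 × 0.30 = 3.0% vs 0.03 + 0.08 × 0.15 = 4.2%, a difference of +1.2 points against +0.8 for all abstinence.
4. For summaries across rounds, flag calls made after a later round's quit day, count each person's abstinence on a given date once, and use person-clustered standard errors. Do not recode the earlier round as a failure: that would penalize components that prompt re-treatment.

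The cost is a change of wording and slightly more analysis work, with no new data. Rates per randomized patient will look lower than rates per initiator.
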